This proposed intervention will not directly deprescribe medications; we will not be randomizing patients to medication discontinuation. Instead, we are testing an intervention to prompt consideration of a clinical decision, analogous to a clinical reminder in the electronic health record prompting the provider to consider appropriate care. We propose an innovative approach to promote medication use review that starts by contacting the patient, not the clinician, yet the ultimate decision remains with the patient-provider dyad.

Study Aim

The study primary aim is to examine the impact of a patient-centered intervention to change provider prescribing (the primary outcome), as determined by the frequency with which medications are either deprescribed or de-escalated. Our primary outcome will be the composite of deprescribing and de-escalation of target medications, identified in pharmacy dispensing records of the Corporate Data Warehouse (CDW).

Hypothesis

The hypothesis is deprescribing will be greater for Veterans receiving the intervention brochure than for those in the historical control group.

Study sites

We will target Veterans at three primary care sites who meet eligibility criteria and are prescribed the target medication at the time of their scheduled primary care visit (in-person, video technology-based, or telephone clinics). These sites were selected based upon ability to recruit adequate samples, geographic variability, and patient population. We will include all PCPs at VA Medical Centers (VAMCs) and Community Based Outpatient Clinics (CBOCs), except for resident clinicians, as these trainees are likely to turn over during the intervention.

Randomization

Previous research, including our pilot study, revealed differences in deprescribing tendencies across providers. Thus, although our intervention intends to engage patients, our study design prioritizes comparisons of patients within the same provider to maximize power. At each intervention site, individual PCPs will be randomized to the sequence of medication cohorts. We will randomize PCPs to one of the three medication groups at the beginning of the first (month 1) and second (month 7) window and assigned them to their

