remaining medication group at the start of the third (month 13) window. Our primary comparisons are between “brochure-intervention” patients and “baseline” patients (matched in terms of eligibility) from the same provider. Each patient will only have one opportunity to receive a brochure, even if they subsequently meet eligibility criteria for receipt of a second, different brochure. This allows equal exposure to the intervention for all Veterans since the impact of a second brochure might be influenced by the first brochure.

Although our primary comparison is between patients of the same provider pre- and post-intervention, we will also collect data at non-equivalent control sites matched by geography who will not receive the intervention; all data on control patients will be from the Corporate Data Warehouse (CDW). Including additional control sites will allow us to address potential temporal trends in deprescribing over the timeframe of our study that are not due to our intervention. The use of separate control sites (rather than randomizing some PCPs at each intervention site to control conditions) was preferred due to concerns about potential contamination across intervention and control conditions within sites. For both the control sites and the pre-intervention baseline period, we will identify patients who would have been eligible for the study; patients meeting criteria for multiple cohorts will be randomly allocated to only one.

Study Cohorts

The intervention cohort will consist of eligible patients in one of the three medication groups with an upcoming PCP appointment during the study enrollment period. We will create a comparison historical control cohorts comprising eligible patients in each medication group who were seen by the same PCPs at the same sites as our intervention cohort eighteen months to one year before our intervention cohort window to allow for comparable follow-up time before the intervention commenced. Patients in the intervention cohorts will be excluded from the historical control cohorts.

Medication Groups

To be enrolled in the study intervention or control cohort, patients needed to meet eligibility criteria for one of three medication-based groups. We have selected three medication-based patient groups based upon variations in 1) type of potentially inappropriate use, 2) medication factors (potential benefit and harms of continued use), and 3) anticipated interest in deprescribing by patients and providers.

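### The plan does not require PCPs with brochure patients to have historical controls, so its same-provider comparison takes in some between-provider information

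*Protocol*

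**What the plan says.** **Who enters.** Protocol, Study sites: "We will include all PCPs at VA Medical Centers (VAMCs) and Community Based Outpatient Clinics (CBOCs), except for resident clinicians". The reason given for leaving residents out is turnover: "as these trainees are likely to turn over during the intervention". The documents set no rule for other PCPs who arrive before or between the enrolment windows.

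**Why the comparison is within provider.** Protocol, Randomization: "Previous research, including our pilot study, revealed differences in deprescribing tendencies across providers", and therefore "our study design prioritizes comparisons of patients within the same provider to maximize power". The same section goes on: "Although our primary comparison is between patients of the same provider pre- and post-intervention". SAP, Interim & Final Analysis, likewise describes brochure and historical patients of one provider, matched on eligibility.

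**How the cohorts are formed.** Protocol, Study Cohorts, restricts controls to patients "seen by the same PCPs at the same sites as our intervention cohort eighteen months to one year before our intervention cohort window". The intervention cohort is "eligible patients in one of the three medication groups with an upcoming PCP appointment during the study enrollment period", with no condition on the PCP.

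**How it is analysed.** Protocol, Statistical Analysis Plan, and SAP, Interim & Final Analysis, specify an HGLM with patients nested in providers, random intercepts and slopes, and robust standard errors. SAP, Endpoints & Covariates, adds provider age, gender and profession. Neither document states provider fixed effects, a within/between split, a filter to PCPs seen in both periods, or a sensitivity analysis on this point.

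**The concern.** The restriction runs one way. Controls of PCPs outside the intervention cohort are dropped, but brochure patients of PCPs without controls are kept. A random-intercept model does not discard a provider seen in one period only. It compares that provider's brochure patients with other providers' controls, giving the contrast a weight that depends on the ICC.

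At stake is the design's own rationale. The same-provider comparison is meant to remove differences in prescribing tendency between PCPs, and unpaired PCPs let part of those differences back in. The control-site analysis (SAP, Other analytical subsets) does not cover this: it looks for time trends at other sites, not for a change in PCP mix at the intervention sites.

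**Working it through.** **1. The plan's own figure.** Inputs from SAP, Statistical Power: brochures 1,990 + 894 + 758 = 3,642; attrition 20%; ICC 0.05; 20 patients per PCP; baseline 4.21%; two-sided alpha 0.05. The design effect is 1 + 19 × 0.05 = 1.95. Effective n per arm is 3,642 × 0.8 / 1.95 = 1,494, with a control group of equal size (assumed). The two-proportion formula gives 81.0% power at 6.55% and a detectable rate of 6.52%, in line with the stated 80% at 6.55%. This route is not unique: splitting 3,642 × 0.8 into two arms with no design effect also gives 6.55%. Nothing below depends on which was used. The detectable difference is 6.55 − 4.21 = 2.34 points.

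**2. How much between-provider difference leaks in.** Linear approximation with m = 20 patients per PCP per period (assumed 1:1) and a share f of PCPs with brochure patients only (assumed; the documents give no turnover figure). With total variance 1, a PCP's period means have covariance c = 0.05. The brochure mean has variance v = 0.05 + 0.95/20 = 0.0975, or v = 0.10 + 0.0475 = 0.1475 with an independent random slope whose variance equals that of the intercept. Generalised least squares then gives

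shift in estimate = f × (1 − c/v) × (rate difference of unpaired PCPs).

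| Model | 1 − c/v | f = 10% | f = 20% |
|---|---|---|---|
| Random intercept | 0.487 | 0.049 | 0.097 |
| Plus random slope | 0.661 | 0.066 | 0.132 |

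Entries under f are points of shift per point of difference. In this approximation the multiplier cannot exceed f itself, the crude share.

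**3. Scale.** A 1-point difference at f = 10% shifts the estimate by 0.05 point, about 2% of 2.34. A 2-point difference shifts it by 0.10 (f = 10%) or 0.19 (f = 20%) with a random intercept, or 0.13 or 0.26 with the slope: 4% to 11% of 2.34. A 2-point excess already means a rate 6.21/4.21 = 1.48 times baseline.

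**4. Logistic check.** Simulation of a random-intercept logistic model with no brochure effect: 182 PCPs (3,642/20), 16 patients per period (20 × 0.8), 250 runs per setting.

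| Unpaired PCPs' OR (assumed) | f | All PCPs: mean OR, rejection | Paired only: mean OR, rejection |
|---|---|---|---|
| 1.0 | 10% | 1.00, 7% | 1.00, 5% |
| 1.0 | 20% | 1.00, 4% | 1.00, 4% |
| 1.6 | 10% | 1.04, 6% | 0.99, 4% |
| 1.6 | 20% | 1.12, 15% | 1.01, 6% |

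Monte Carlo error of the rejection rates is roughly 1.2 to 2.3 points. Here the ICC of 0.05 is on the logit scale, which is weaker clustering on the probability scale at a 4% rate, so the leak is larger than in step 2. The simulation shows the mechanism and that restriction removes the bias. It is not a second estimate of size.

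**5. How many PCPs could be unpaired.** The text allows two readings of the historical window. If it is anchored to each cohort window, controls for the window starting at month 13 fall at about months −5 to 1, and a PCP needs to have been in post about 12 months before that window. If it is anchored to study start, the same PCP needs about 24 months. The 10% to 20% used above is not derived from either reading.

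**The case against.** The strongest reply is that a between-provider component is not yet a bias. The protocol says that PCPs differ, not that newly arrived PCPs differ as a group, and where they do not, step 4 shows none. This stands.

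A reader might infer that newcomers deprescribe more when they take over a panel, so that the brochure effect is inflated. No passage supports this; if they deprescribe less, the sign reverses.

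Second, PCPs are randomized to a sequence from month 1, which suggests a roster fixed early. Under per-window anchoring, most PCPs would then have some historical patients. This is plausible, but joiners are not barred and the anchoring is not settled.

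Third, provider age, gender and profession are in the model and may absorb part of any difference. They may, though none of them is tenure, and the calculations above give them no credit.

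Fourth, calling the comparison same-provider could be taken to mean that unpaired PCPs drop out. That may be the intent, but no sentence says so and the stated model does not do it.

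A reader might also fault PCP eligibility for lacking a tenure rule. Broad inclusion suits a real-world hybrid trial. The gap lies in the analysis specification.

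**Conclusion.** The gap is real and modest. The stated model does not fully deliver the stated same-provider comparison, because brochure-only PCPs contribute between-provider information. The documents do not establish that the result is biased, in which direction, or how many PCPs are involved. At ICC 0.05 with 20 patients per PCP per period, the sensitivity is about 0.05 point (10% unpaired) to 0.10 point (20%) per point of difference, or 0.07 to 0.13 with an equal-variance random slope. It would approach the 2.34-point detectable difference only if many PCPs were unpaired and their rates were far from those of established PCPs. The change is worth making because it is cheap and carries out the comparison the plan already names.

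**What to change.** Leave PCP eligibility unchanged. In the SAP, under Interim & Final Analysis:

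- Estimate the primary effect within provider by one of two routes: (a) limit the primary comparison to PCPs with at least one eligible patient in both periods; or (b) keep all patients and add the PCP-level proportion of brochure patients to the HGLM, so that the brochure coefficient reflects the within-provider contrast.
- Report the all-PCP model without that term as a sensitivity analysis.
- Report the number of one-period PCPs and of their patients.
- State whether the historical window is anchored to each cohort window or to study start.

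The SAP is written in the past tense. If the analysis has already been run, date the change and show both results.

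**Cost.** Route (a) removes about 364 (10%) to 728 (20%) of the 3,642 projected brochure patients from the primary set under the assumed shares, and narrows it to established PCPs. The standard error rises by 1.2% or 2.5% with a random intercept and by 2.3% or 4.8% with the equal-variance slope. The SAP-style formula, with effective n of 1,494 × 0.9 = 1,345 or 1,494 × 0.8 = 1,195 per arm, takes power from 81% to 77% or 72%. That is an upper bound on the loss, because the formula gives no credit for pairing and the missing controls are absent either way. Route (b) keeps every patient at the price of one extra model term.

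### Patients eligible for several target drugs enter the brochure and historical groups under different written rules and may be over-represented in the brochure group

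*Protocol*

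**What the plan says.** Brochure group. The Protocol (Randomization) states that "individual PCPs will be randomized to the sequence of medication cohorts". Windows open at months 1, 7 and 13, and the third takes whichever drug group remains. A cap applies: "Each patient will only have one opportunity to receive a brochure". The Protocol (Study Cohorts) defines the intervention cohort as "eligible patients in one of the three medication groups with an upcoming PCP appointment during the study enrollment period".

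Historical group. The Protocol (Randomization) says "For both the control sites and the pre-intervention baseline period, we will identify patients who would have been eligible for the study", and for these patients only, "patients meeting criteria for multiple cohorts will be randomly allocated to only one". The Protocol (Study Cohorts) takes them from patients "seen by the same PCPs at the same sites as our intervention cohort eighteen months to one year before our intervention cohort window", and removes from the historical cohorts anyone who is in an intervention cohort.

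The Protocol describes the two groups as matched on eligibility. The SAP (Endpoints & Covariates) lists patient age, race, sex and Elixhauser comorbidities, plus provider characteristics, as covariates. The number of target drug groups a patient qualifies for is not listed.

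**The concern.** A patient eligible for one target drug has one relevant brochure window. A patient eligible for two has two: a patient with no appointment in the first can still enter in the second. In the historical period, the written rule assigns the same kind of patient to a single cohort. If that leaves one chance of entry, the same PCP panel yields a larger share of multi-drug patients in the brochure group than in the historical group.

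This matters if multi-drug patients are deprescribed at a different rate after adjustment. Part of the before-and-after difference would then reflect case mix. Comparing within provider does not help, because the asymmetry operates inside each PCP's panel. The control-site trend analysis in the SAP (Other analytical subsets) does not help either, because control sites use the random-allocation rule and have no brochure windows.

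**Working it through.** **The plan's own figure.** From the SAP (Statistical Power): 1,990 + 894 + 758 = 3,642 brochure patients, 20% attrition, ICC 0.05, 20 patients per provider. The design effect is 1 + 19 × 0.05 = 1.95, so the effective size is 3,642 × 0.8 / 1.95 = 1,494 per group, taking equal groups. Power for 4.21% against 6.55% is then 0.81, which agrees with the stated 80%. The smallest detectable difference is 6.55 − 4.21 = 2.34 points. The standard error of the difference is √[(0.0421 × 0.9579 + 0.0655 × 0.9345) / 1,494] = 0.82 points.

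**Entry.** Let p be the chance of a visit in a six-month window, assumed independent across windows. The documents give no value.
- One-drug patient: p in either group.
- Two-drug brochure patient: 1 − (1 − p)².
- Two-drug historical patient, common window or allocation before window matching: p.

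The entry ratio for two-drug patients is [1 − (1 − p)²] / p = 2 − p, that is 1.5, 1.3 and 1.1 at p = 0.5, 0.7 and 0.9. It is 1.0 if every patient has a visit in every window.

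**Shares.** Let s be the two-drug share in the historical group (assumed). The brochure share is s(2 − p) / [s(2 − p) + (1 − s)].

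| s | p | Historical | Brochure | Gap (points) |
|---|---|---|---|---|
| 20% | 0.5 | 20.0% | 27.3% | 7.3 |
| 20% | 0.7 | 20.0% | 24.5% | 4.5 |
| 20% | 0.9 | 20.0% | 21.6% | 1.6 |
| 10% | 0.7 | 10.0% | 12.6% | 2.6 |
| 5% | 0.9 | 5.0% | 5.5% | 0.5 |

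**Shift in the crude contrast** = gap in shares × difference in deprescribing rate between two-drug and one-drug patients (assumed).
- s = 20%, 4-point difference: 0.29, 0.18 and 0.06 points at p = 0.5, 0.7 and 0.9.
- s = 5 to 10%, 2-point difference, p = 0.7 to 0.9: 0.01 to 0.05 points.

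**Removal of brochure patients from the historical cohort.** Suppose a proportion r = 0.7 of historical patients are still eligible later (assumed). One-drug patients are then removed with probability r·p and two-drug patients with probability r·[1 − (1 − p)²].
- s = 10%, p = 0.8: the historical share is 0.1 × 0.328 / (0.1 × 0.328 + 0.9 × 0.44) = 7.6%, against 11.8% in the brochure group.
- s = 10%, p = 0.6: 7.3% against 13.5%.
- s = 20%, p = 0.5: 15.4% against 27.3%, a gap of 11.8 points before rounding. With 4.21% overall and a rate ratio of 2, one-drug patients have 4.21 / 1.2 = 3.51%, so the rates differ by 3.51 points and the shift is +0.42. With a ratio of 0.5 the rates differ by −2.34 points and the shift is −0.28. Without the removal these two shifts are +0.26 and −0.17.

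**Alternative reading.** If historical windows follow the drug windows, and allocation is only among cohorts for which the patient had a qualifying visit, historical entry is also 1 − (1 − p)². With s = 10% of the panel the shares are 11.8% in both groups at p = 0.8, and 13.5% in both at p = 0.6. There is no imbalance before the removal step. With r = 0.7 and p = 0.8, the removal alone would still lower the historical share to 0.1 × 0.96 × 0.328 / (0.1 × 0.96 × 0.328 + 0.9 × 0.8 × 0.44) = 9.0%.

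**Which reading fits better.** The Protocol (Study Cohorts) places the historical period so that follow-up is comparable and precedes the intervention. Counting from the start of month 1, the third window opens at 12 months. A period 18 to 12 months earlier runs from −6 to 0, and its six-month follow-up ends between 0 and +6, after mailing began. That favours one common window but does not settle it, because the text could mean the start of each drug's own window.

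**The case against.** The strongest objection is that the documents do not establish the imbalance. They do not say whether the historical period is common or per drug window, or whether allocation comes before or after window matching. Under one permissible reading the shares agree before brochure patients are removed. This stands, and it is why the point is worded as a possibility.

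The size is also open to challenge. A 4-point difference is nearly the whole 4.21% baseline. With a 20% share it implies about 3.4% in one-drug and 7.4% in two-drug patients, a ratio of 2.2, for which the documents give no support. The 20% overlap has no source either. If multi-drug patients have more contacts, their p is higher and the ratio 2 − p moves towards 1. All of this stands, so the upper figures are bounds under assumption and not estimates.

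The 2.34-point benchmark is the smallest detectable difference. It is not the expected effect: the SAP calls a 15% rate reasonable to expect. Against 15 − 4.21 = 10.79 points, or 15 − 10 = 5 points at the SAP's higher baseline, a shift of 0.29 is about 3% or 6%.

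Two further inferences should be resisted. Multi-drug patients are not counted twice, because the one-brochure cap prevents it. Nor is the overall drug mix distorted: averaged over random PCP sequences, two-drug brochure patients split evenly between their two drugs.

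What survives is the difference in the written rules, the removal step that can add to it, and the absence of any covariate that captures it directly.

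**Conclusion.** The entry rules for multi-eligible patients differ as written, and the plan does not show that the resulting groups are comparable on this point. Over-representation in the brochure group follows if some patients have no visit in a given window and the historical cohort is one common window or is allocated before window matching. The removal of brochure patients can widen the gap.

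The probable effect on the primary contrast is small: roughly 0.01 to 0.3 points in absolute size before the removal, and up to about 0.4 points with it at rate ratios between 0.5 and 2. The larger figure is about 18% of the 2.34-point smallest detectable difference (0.42 / 2.34) and half a standard error (0.42 / 0.82). Overlap, visit probability, independence of visits, retention and rate difference are all assumptions.

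A reader might infer that the imbalance is certain, or that it inflates the brochure effect. The documents support neither. They leave the window rule open and give no deprescribing rate for multi-drug patients, so the direction is unknown. The point justifies an inexpensive safeguard and does not undermine the primary analysis.

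**What to change.** 1. Using the same code in both groups, derive for each patient the number of target drug groups (1, 2 or 3) for which the patient qualifies at the index visit.
2. Tabulate that count by group. If there is no imbalance, the table will show it.
3. Add the count as a covariate to the primary hierarchical model.
4. Add a sensitivity analysis limited to patients eligible for one group only, where the entry rules agree.
5. State whether the historical window is common or per drug window, and whether allocation to a cohort precedes or follows window matching.

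The cost is one derived variable from the CDW data already used for eligibility, one rerun of the model and a few sentences of text. The sensitivity analysis loses the multi-eligible patients and so some precision. The SAP's power figure does not change.

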We will query CDW for 6 months following the date of each scheduled primary care visit to assess our primary outcome of deprescribing. Based upon findings in our pilot study, medication orders may not be discontinued in electronic health records even if discussions occur in the clinic visit (e.g., the PCP tells the patient to deprescribe but does not change the order). Notably, because our primary objective is to improve safe prescribing and reduce PIMs, pharmacy dispensing data best reflects our deprescribing outcome. As per our definition, either complete cessation or dose reduction will be fulfillment of our primary outcome.

Modeling our approach after the methods of Steinman, Sussman, and Martin, we will use non-refill of the medication in the 6 months following the primary care appointment as our a priori definition of cessation, based upon dispensing dates.^{4,5} Per VA Pharmacy policy, medications are only refilled upon request, and therefore, non-refill of a medication can indicate that it was discontinued, it expired (typically one year after it was ordered), or the patient did not refill it. If the medication continues to be dispensed, we will determine any reduction in the total daily dose, indicating de-escalation (one component of our deprescribing definition). An

exception to the de-escalation rule will be for insulin, where only complete cessation will qualify since dose changes are less likely to be reflected in the order compared to oral medications.

Consistent with our conceptual framework, we will also assess patient and provider factors that may influence deprescribing. Patient factors will be obtained from CDW, and will include age, race, sex, Elixhauser comorbidities in the two years prior to the scheduled primary care visit. Provider factors include sex, discipline, age, and site.

To assess potential ADWEs, we will ascertain if the deprescribed medication is subsequently restarted or returns to original dosing. We will then query CDW for diagnoses of GI bleeding for the PPI cohort, diabetic ketoacidosis or hyperosmolar hyperglycemic state for the DM cohort, and seizure for the gabapentin cohort in the year following the index visit. Note, we consider substitution to a lower potency medication (e.g., histamine-2 receptor antagonist for a PPI) to be a neutral or desirable event and not an ADWE.

Statistical Analysis Plan (see attached statistical analysis plan for greater detail)

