Official Title: Engaging Patients to Promote Deprescribing

NCT Number: NCT04294901

Document Date: November 14, 2019

Statistical Power

Based on fiscal year (FY) 2017 data, we estimated that we would mail brochures to at least 1,990 PPI patients, 894 Diabetes-Hypoglycemia patients, and 758 Gabapentin patients during the study. For apriori statistical power analyses, we made the following assumptions based on our pilot data: an overall baseline deprescribing rate of 4.21%, a conservatively high intraclass correlation coefficient (ICC) of 0.05 (for non-independence among patients of the same provider), an average of 20 eligible patients per PCC or WHC provider, and a 20% attrition rate (i.e., patients who receive the intervention brochure but do not attend their clinic visit). With these assumptions, we determined that we would have 80% power (for two-tailed tests at $\alpha=0.05$) to detect deprescribing rates following the intervention as small as 6.55% overall for these low-end estimates of our projected sample. Moreover, even at these low-end estimates of the projected sample size, we determined we would have 80% power to detect an overall deprescribing rate as low as 15% among the combined intervention cohorts even if the ICC was as high as 0.1, the baseline deprescribing rate was as high as 10%, and/or the attrition rate was as high as 40%. Notably, a deprescribing rate of 15% was reasonable to expect given that we found similar or higher rates in our pilot study.

We conducted analyses using SAS.³

Endpoints & Covariates

The primary hypothesis was deprescribing would be greater for Veterans receiving the intervention brochure than for those in the historical control group.

The primary outcome was binary: deprescribing versus not, assessed via pharmacy dispensing data from the VA Corporate Data Warehouse (CDW). More specifically, six months from the index date, an analyst queried the CDW to determine medication outcomes (e.g., complete deprescribing, dose reduction). We selected 6 months because prescriptions are often filled as a 90-day supply and using a shorter observation window might not fully identify that the prescription was not refilled. We removed patients who died within six months from their index data from intervention and historical controls at the analysis stage to avoid misattributing deprescribing to the intervention rather than death.

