To identify dose reductions, we calculated the total daily dose (TDD) of the target medication as [dose*(quantity/days supplied)].^{1,2} Substitutions within a medication drug class (e.g., pantoprazole to omeprazole) were standardized to one medication within each class. We only compared TDD at 6 months to that at the index visit for oral medications because insulin dose adjustments are not consistently documented within the electronic health record. Combination insulin products were separated into their long acting and short acting components and analyzed separately. We allowed a 10% buffer for days' supply of PPI, sulfonylurea, and gabapentin (e.g., 33 days for a 30-day supply) to account for missed doses and 100% buffer for insulin due to dispensing requirements (e.g., minimum vials dispensed regardless of dose).

Patient factors and provider characteristics (age, gender, profession) were included as covariates in the model. Based on our conceptual model and using data from CDW, patient factors included age, race, sex, and Elixhauser comorbidities in the year prior to the scheduled primary care visit.^{4,5}

Additionally, we planned to examine whether the effectiveness of the brochure intervention was associated with target medication.

Interim & Final Analysis

Our primary comparisons were between “brochure-intervention” patients and “historical control” patients (matched in terms of eligibility) from the same primary care provider. To investigate the impact of the intervention brochure on deprescribing, Hierarchical Generalized Linear Modeling (HGLM) was used to account for the nesting of patients within providers. This approach provided information not just about the average effectiveness of the intervention, but also about how much variation there is in the intervention impact across providers. In all models, Level 1 (patient-level) intercepts and slopes were treated as random effects, and parameters were estimated with robust standard errors. Using this approach of nesting patients within providers at intervention sites, for our primary analysis, we compared the likelihood of deprescribing among patients in the pre-intervention (“historical”) period to that for patients in the intervention periods who were mailed the brochure. We predicted that intervention patients would be significantly more likely to have deprescribing than patients in the pre-intervention period with the same eligibility criteria. We then examined whether the

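### Intervention patients enter on a booked appointment and are analysed if mailed, historical controls are described as seen, and no text says whether controls who missed their visit are kept

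*Protocol*

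**What the plan says.** **Intervention side.** The Protocol (Study Cohorts) takes "eligible patients in one of the three medication groups with an upcoming PCP appointment during the study enrollment period". Under Procedures to Minimize Risk, brochures go out two weeks before the visit, so attendance cannot be an entry condition. The SAP (Interim & Final Analysis) states the primary comparison "for patients in the intervention periods who were mailed the brochure".

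**Historical-control side.** The next sentence of Study Cohorts takes eligible patients "who were seen by the same PCPs at the same sites as our intervention cohort". Intervention patients are barred from this cohort.

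**Non-attendance.** The SAP (Statistical Power) assumes 20% attrition, defined as "patients who receive the intervention brochure but do not attend their clinic visit", and also considers 40%. It does not say whether these patients leave the analysis, and it gives no counterpart for controls.

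**Removals at the analysis stage.** The SAP (Endpoints & Covariates) states one: "We removed patients who died within six months from their index data from intervention and historical controls at the analysis stage".

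**Text pointing to one rule for both groups.**
- Protocol, Study sites: the target population is Veterans "who meet eligibility criteria and are prescribed the target medication at the time of their scheduled primary care visit".
- Protocol, Randomization, on control sites and the baseline period: "we will identify patients who would have been eligible for the study".
- Protocol, Study Measures: "We will query CDW for 6 months following the date of each scheduled primary care visit".
- The SAP dates comorbidities from the scheduled visit and says the pre-intervention patients met the same eligibility criteria.

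**The concern.** The primary contrast is a non-randomised before-and-after comparison within provider. Its validity depends on selecting patients in the same way in both periods. Two adjacent sentences tie entry to different events: a booked visit on one side and, on the ordinary meaning of *seen*, a completed visit on the other. A programmer who followed both literally would keep mailed no-shows in the intervention group and have no no-shows among the controls.

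The outcome could well differ by attendance. Study Measures counts any non-refill in six months as cessation, including an expired order or a patient who simply did not refill. No-shows may score low because no conversation took place, or high because nothing was renewed. The listed covariates do not include attendance, so the model would not remove the difference. What is at stake is a shift in the primary estimate that has nothing to do with the brochure.

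**Working it through.** **1. Inputs from the SAP (Statistical Power).** Mailed: 1,990 + 894 + 758 = 3,642. Baseline rate 4.21%; detectable rate 6.55%; ICC 0.05; 20 patients per provider; attrition 20%; two-sided alpha 0.05. Design effect = 1 + (20 − 1) × 0.05 = 1.95.

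**2. The SAP's own figure.** The method is a two-proportion normal approximation, with pooled variance for the critical value. The SAP gives no control-group size, so 1:1 is assumed. With 20% lost from both groups, effective n = 3,642 × 0.80 / 1.95 = 1,494 per group. The standard errors are 0.826 points (pooled) and 0.824 (unpooled), so z = (2.34 − 1.96 × 0.826) / 0.824 = 0.88 and power is 0.81, against 80% stated. The figure reproduces. Losing 20% from the intervention group only gives 0.851, and losing nobody gives 0.887.

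**3. Shift under the literal reading, with no brochure effect.** Let a be the attender rate and b the no-show rate.
- Intervention rate = 0.80a + 0.20b
- Control rate = a
- Shift = 0.20 × (b − a)

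**4. Numbers put in.** Assumptions that are not in the documents: the values of b; a = 4.21% (the SAP calls this an overall baseline rate); and 2,914 seen controls (80% of 3,642). Effective sizes are 3,642 / 1.95 = 1,868 and 2,914 / 1.95 = 1,494. The last column is the chance of a significant result in the direction of the shift; nominal is 2.5%.

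| b | Intervention rate | Shift (points) | False-result chance |
|---|---|---|---|
| 0% | 3.37% | −0.84 | 25.0% |
| 3% | 3.97% | −0.24 | 5.5% |
| 4.21% | 4.21% | 0 | 2.5% |
| 5% | 4.37% | +0.16 | 4.1% |
| 6% | 4.57% | +0.36 | 7.2% |
| 8% | 4.97% | +0.76 | 17.6% |

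For scale, the SAP's detectable difference is 6.55 − 4.21 = 2.34 points.

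**5. Sensitivity.** With 2,400 to 3,642 controls, the chance at b = 0% runs from 23% to 27%, and at b = 8% from 16% to 20%. If 4.21% is instead the rate among all scheduled patients, the attender rate is (4.21 − 0.20b) / 0.80, which is 5.26% at b = 0% and 3.26% at b = 8%. The shifts become −1.05 and +0.95 points, with chances of about 30% each. At the SAP's 40% attrition scenario the step 3 shifts double.

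**6. Power if non-attenders are kept in both groups.** Assume that 4.21% and 6.55% apply to attenders, that non-attenders have 4.21% in both periods, and that each group has 3,642 patients (control size assumed). The intervention rate is 0.80 × 6.55 + 0.20 × 4.21 = 6.08%, and the difference is 1.87 points. With effective n of 1,868 per group, z = (1.87 − 1.96 × 0.723) / 0.722 = 0.63 and power is about 0.74.

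Steps 4 to 6 use an unadjusted test with a design effect, not the planned covariate-adjusted hierarchical model. They show order of magnitude only.

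**The case against.** The asymmetry rests on one word. The scheduled-visit target population, the baseline patients who would have qualified, the follow-up clock and the SAP's shared eligibility criteria all suggest one appointment-based rule, with *seen* as loose wording. This stands, and it is why bias cannot be asserted. It does not close the point, because none of those passages mentions a control who did not attend, and *seen* is in the sentence that builds the control cohort.

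A second symmetric reading is that attenders are compared with attenders. Attrition usually means loss from the sample, and the SAP's power is matched best when 20% is removed from both groups. But the SAP's primary analysis refers to patients mailed the brochure, which weighs against this reading, and a power calculation does not show how the analysis set was built.

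The magnitudes are also open to challenge. A no-show rate of 0% is hard to square with an outcome that counts every non-refill, and 8% is nearly twice baseline. At 3% to 6% the false-result chance is only about 4% to 7% away from equality. That is fair, and the narrower range deserves equal weight.

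A reader might go further and infer that controls were in fact drawn from completed visits, that the contrast favours the brochure, or that the power figure is wrong. The documents support none of these. They do not report how the query was run, they give no outcome rate for no-shows, and the power figure reproduces.

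**Conclusion.** The concern holds as an unreconciled definition of the primary comparison groups that could produce bias. It does not show that bias occurred. If the text is followed literally, the shift with no brochure effect is about −0.24 to +0.36 points for no-show rates of 3% to 6%, and −0.84 to +0.76 points for 0% to 8%. At the wider extremes that is about a third of the 2.34-point detectable difference. These figures rest on 20% non-attendance, an attender rate of 4.21% and no-show rates that the documents do not give. The shift is zero if no-shows and attenders have the same rate, and it does not arise if both groups were drawn from scheduled visits. The point should be fixed because it concerns the primary contrast and is cheap to settle. Confidence is medium, since several passages favour the symmetric scheduled-visit reading.

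**What to change.** Define the intervention, historical-control and control-site cohorts by the same CDW rule: eligible patients with a scheduled primary care appointment, indexed on the scheduled date and kept whether or not they attended. Replace *seen* in Study Cohorts accordingly. State in the SAP that non-attenders stay in the analysis in both periods.

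Because they then stay in, restate the power section instead of treating the 20% as lost. Step 6 of the working gives about 0.74 under its assumptions; the sponsor should substitute the actual control-group size and its own assumption for non-attenders.

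Optionally, report attendance by period and repeat the analysis in attenders of both groups. That should be a sensitivity analysis only, because attendance comes after mailing and may be affected by it.

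**Cost.** Wording plus a revised power statement if controls were already drawn from scheduled visits. If they were drawn from completed visits, the historical and control-site queries must be rerun. The documents do not say whether CDW keeps missed historical appointments in usable form, so the sponsor should confirm this. The price of the common rule is a diluted effect, from 2.34 to 1.87 points under the assumptions shown.
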